WTS refers to a cluster of symptoms reported in case studies by Pierpont.(1) In that series individuals reported sleep disturbance, headache, tinnitus (ringing in the ears), a sensation of pressure in the ears, dizziness, vertigo, nausea, visual blurring, palpitations, irritability, problems with concentration and memory and panic episodes associated with sensations of internal pulsation or quivering when awake or asleep.(1) In that report, the symptoms typically improved during holidays or other withdrawal from the wind turbine environment and returned with re-exposure. There are case reports of WTS being present in one family member but not in another who lives in the same dwelling.(2) It has been proposed that people who are particularly ‘sensitive’ to noise may be at greatest risk. It has been argued that WTS is caused by infrasound generated by wind turbines.(1, 3, 4)

Alternative Explanations

Some experts have discounted the association between the symptoms of WTS and exposure to noise from wind turbines. They suggest the symptoms are the result of a nocebo effect, in which a patient can be convinced that something benign is making them sick. It is argued that the annoyance and health effects some people experience when unwanted turbines are erected in their local areas are more strongly related to subjective factors such as the visual impact of the turbines, attitudes towards wind energy and whether there is economic benefit from turbines, rather than to noise itself, both audible and inaudible (i.e. infrasound).(4, 5) This level of annoyance may be the primary mediating agent causing sleep disturbance and increased psychological distress.(6) Stress is considered another mechanism by which noise can impact on human health.(7) Where stress effects are present, they may be dependent on the level of annoyance induced by the noise.(8)

Noise from wind turbines

Wind turbine noise comprises the following range of spectra of relevance to this study:

- i. Infrasound (frequencies less than 20 Hz),
- ii. Low Frequency (LF) sound (frequencies 20-200 Hz)
- iii. High Frequency (HF) sound (frequencies above 200 Hz).

Whilst infrasound is regarded as being below the audible range, if its level is high enough it can be “sensed”. This sensation is best described as a sensation of pressure on the ears(9) or a sensation or sound of deep humming/rumbling.(2) There is no sense of pitch attributable to infrasound. In contrast, noise in both the LF and HF range is usually audible with a sense of pitch.

Wind turbine noise encompasses the whole of the sub-audible and audible frequency spectrum – infrasound, LF sound and HF sound including amplitude modulation (“swish”) effects of the higher frequency sounds. It is not known which of those components contribute to annoyance and which contribute to the alleged health effects.

Infrasound

The nature of infrasound is now well understood(10) based on acoustical studies performed at Bluff Wind Farm (SA), Cape Bridgewater Wind Farm (VIC) and Shirley Wind Farm (USA).(11) The sound is comprised of the blade pass frequency (typically 0.7-0.8Hz) and its harmonics. The maximum sound pressure level at these frequencies was 89.5dB Lin Peak (recorded at Shirley Wind farm).

Community concerns are focused on infrasound

The main community group advocating that wind farms have deleterious effects on health is the Waubra Foundation. The foundation’s chair, [name] recently served as an observer on the NHMRC Wind Farms Health Effects Reference Group. The foundation recently published a statement “Acoustic Engineering Investigation into Airborne and Ground-Borne Pressure Pulses from Wind Turbines at Cape Bridgewater”(12) ([name], personal communication to [name]) which summarises their concerns. It states that although infrasound is only audible at very high levels, “it can be damaging to the human body at levels well below audibility”. Moreover the document states that “Infrasound has long been known to be dangerous and harmful to humans, especially with chronic exposure. Infrasound persists for much greater distances than audible sound and, unlike audible sound, penetrates virtually all building structures (including double glazing) with ease; and often increases the impact by resonating with internal structures in the house”. While infrasound is ubiquitous, anti-wind farm community groups state that wind turbines have a specific infrasound signature or profile that differs from common sources of infrasound such as ordinary wind, household appliances or waves on a beach. This profile is “a necessary tool for investigating noise from wind turbines anywhere”.

In addition, the foundation recommended that research also measure subjective “sensation” of vibration related to infrasound by use of specific self-report scales, investigation be undertaken inside houses and continue over sufficient periods of time, such

as 6 weeks. It is the infrasound component of the noise that is claimed by those suffering nausea, dizziness and other symptoms that is the primary cause of their symptoms.

Given these views from community groups and the lack of high quality research on health effects identified by the NHMRC Reference Group,(13) we propose that the correct approach to addressing the issue of wind farm noise and health effects is to focus on robustly assessing the effects of infrasound using a synthesised sound that matches the infrasound profile of wind farms in a randomised controlled trial of exposure.

Possible biological mechanism for vestibular effects

The following observations indicate that infrasound may be capable of producing audio vestibular disturbances, particularly in susceptible individuals.

1) At very low frequencies, the cochlear outer hair cells (innervated by type II afferents which do not participate in conscious hearing) are stimulated by sounds below the audible range.(14)

2) Structures involved in endolymph volume regulation are influenced by infrasound. In experimental animals, brief (1-2 min) exposures in the moderate to intense ranges of low frequency tones have induced endolymphatic hydrops.(15)

3) Humans, monkeys and guinea-pigs do not show evidence of vestibular activation by high levels of infrasound(16) but some inner ear pathologies lower the thresholds for vestibular activation due to the presence of an additional low resistance pathway or “third window”: superior semicircular canal dehiscence, large vestibular aqueduct syndrome.(17, 18) Further, endolymphatic hydrops and vestibular migraine, which are characterized by sound hypersensitivity, may also provide additional biologically plausible pathways by which infrasound may have health effects. Hence, there is a biologically plausible mechanism for the physiological effects of infrasound. However, as yet there is no evidence that these effects actually occur. The study proposed here is designed to provide data in this area.

Noise sensitivity and annoyance

Noise sensitivity and annoyance are considered to be related but not identical concepts.(19) Noise sensitivity is a distinct psychological trait and refers to the predisposition to perceive noisy events. Annoyance is an attitudinal dimension indicating the extent to which noises are evaluated unfavourably.(20) About 20-30% of individuals self-describe as noise sensitive. Although noise sensitivity does not differ by sex, it tends to increase with age.(21) Noise-sensitive individuals have noise “annoyance thresholds” approximately 10 dB lower than noise tolerant individuals(22) and usually react to environmental sound more easily, evaluate it more negatively, and experience stronger emotional reactions compared to noise tolerant people.(23) People who are noise sensitive are more likely than others to report annoyance due to exposure to sound at low and moderate intensity.(24) Noise sensitivity and annoyance are usually measured by self-report questionnaires. In this study, we will selectively recruit subjects who report increased noise sensitivity and measure annoyance from study exposures in each study arm.

2. Study Objectives

To investigate whether six month infrasound exposure, compared with the sham exposure, is associated with impaired sleep quality (the primary outcome, measured as wake after sleep onset, WASO), an excess of symptoms that have been attributed to Wind Turbine Syndrome, annoyance, sleepiness, impaired neurobehavioural and neurocognitive performance, impaired vestibular function, increased arterial stiffness and increased blood pressure (secondary outcomes).

Secondly, to investigate whether experiencing an excess of symptoms that have been attributed to WTS is related to baseline levels of stress and anxiety.

A complementary short-term laboratory-based study is underway to measure the short term health effects of exposure to infrasound, sham (negative control) and traffic noise (positive control). <http://www.ANZCTR.org.au/ACTRN12617000001392.aspx>

3. Experimental design

This community based randomised controlled trial has two parallel groups and will be conducted within the homes of non-metropolitan participants:

- 1) simulated wind turbine sound (infrasound, test exposure)
- 2) absence of sound (sham, control exposure).

Participants will be randomised to either the infrasound or sham exposure. Four speakers that are visually identical but that deliver either infrasound or sham will be installed in the bedrooms of participants. Participants and research staff conducting clinical assessments will be blinded to the test and control exposure (as the infrasound is inaudible). The members of the team who will be unblinded are the acoustic engineers who install the speakers in the home, conduct checks and maintenance and the chief investigators responsible for the randomisation schedule.

The speakers will be in place for six months and clinical outcome assessments will be conducted at the three month and six month time points.

4. Methods: Participants, interventions, and outcomes

Study setting

Non-metropolitan sites anywhere within NSW, will be selected based on a process that takes into consideration:

- 1) Location – the site is in a region conveniently located to minimise travel time from Sydney for the researchers.
- 2) Topography – the landscape of the site will be similar to the type of environment where wind farms are usually constructed.

An example of a region of interest is The Southern Highlands, south-west of Sydney, because it satisfies the two requirements listed above.

Firstly, it is only 110 kilometres from Sydney, allowing for a relatively short travel time.

Secondly, the Southern Highlands have the potential for high winds because the region lies along the elevated section of the Great Dividing Range. Therefore, certain locations in this region have the optimal combination of average wind speeds that are high and consistent, as well as flat landscapes, making it an ideal location for a wind farm. There are currently no wind farms present in the region; the closest is the Taralga Wind Farm that is approximately 50 kilometres from Bowral.

We are also interested in recruiting in the Camden/Macarthur region as areas closer to Sydney as well as the population density being somewhat similar to population densities around windfarms. This area is also more than 50 kilometres away from an already existing windfarm.

5. Eligibility criteria

5.1 Inclusion criteria

1. Aged 18 or above **(If you consent to participate in this study you agree that persons under the age of 18 will not be permitted to sleep in the bedroom where the speakers are installed)**
2. Noise sensitive individuals -defined as Weinstein's Noise Sensitivity Scale (WNS) Score >58 (Appendix B)
3. Normal hearing
4. Regular sleep of 5.5 hours / 24 hours for 7 days as demonstrated by actigraphy
5. Fluent in English, to be able to answer computerised questionnaires and undergo neurocognitive assessments in English

5.2 Exclusion criteria

1. Rotating shift worker
2. Planning to be away from home for more than a month during the study period

3. Major psychiatric disorders
4. Use of any hypnotic medications or other medications that interfere with sleep within the last month
5. Breastfeeding, pregnant or attempting to become pregnant women in the household
6. Young children (under 5 years) living in the home

6. Study Interventions

Participants that meet the eligibility criteria will be randomised to either:

- 1) simulated wind turbine sound at 93dB Pk (infrasound, test exposure)
- 2) absence of sound (sham, control exposure).

Four 600mm x 600mm cube speakers (photo below) will be installed in the bedroom of each participant. For participant convenience, these speakers can be placed in variable configurations within the participant's bedroom. The speakers are wired together and are powered by a single cord that plugs into a domestic power point.

In addition to the speakers there will be two microphone stands with microphones placed in the bedroom. Neither microphone will collect sound content or conversation, but they will collect the sound level in decibels of 1) infrasound and 2) audible sound.

The speakers and microphones will operate continuously over the six month period of the study. By agreement with the participant, the acoustic engineer will schedule regular visits to the home to assess the correct functioning of the equipment. These visits may be up to weekly in the first month of operation and then monthly or as required for the remaining five months of operation. All participants will be reimbursed for expenses associated with the use of electricity to run the speakers. The acoustic engineer will be unblinded to group allocation and will be the contact point for participants who want to discuss anything regarding the speakers, microphones, electricity consumption or other exposure related query, thus ensuring the participant and clinical assessment staff remain blinded to group allocation.

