6.1 Discontinuing

Withdrawal criteria

Participants will be informed that they have the right to withdraw from the study at any time, without prejudice to any medical care (such that might be required if we incidentally identify a medical condition), and are not obliged to state their reasons. Additionally the investigator may withdraw a participant at any time for the following reasons:

- If any of the study exclusion criteria are diagnosed
- Protocol violations
- Adverse events

Discontinuation of the study

The study may be discontinued at any time on the advice of the responsible principal investigators on the basis of new information regarding safety. A Data Safety Monitoring Board has been constituted to provide advice to the investigator team with regard to participant safety (Section 15.1). Additionally, the study may be terminated if progress is unsatisfactory.

In the case of premature termination or suspension of the experiment, the investigator will inform the study participants and ensure appropriate follow up in the unlikely event this is required clinically. In addition, the appropriate ethics committee will be informed.

Procedure to withdraw

Participants with clinically significant abnormalities requiring discontinuation will be followed until recovery from the abnormality. If the study is discontinued for safety reasons, the investigators will contact all affected participants within a week to inform them of the termination of their involvement in the study. Participants discontinuing from the study may be replaced. A new participant number must be issued for the new participant.

If a participant fails to respond to telephone contact or is consistently unavailable for home visit, attempts will be made to ensure that the reason for not communicating is not an adverse event (bearing in mind that the participant is not obliged to state his/her reasons).

7. Outcomes

Primary outcome measure:

Changes in wake after sleep onset (WASO) as determined by 4 EEG channel polysomnography with portable recorder at baseline, 3 and 6 months. We will compare the differences between infrasound and sham sound.

Secondary outcome measures:

EEG parameters from the overnight sleep studies - Sleep latency, sleep staging, sleep stage shifts, arousal frequency and power spectral analysis for sleep microarchitecture analysis.

Tertiary Outcome Measures:

Neurocognitive tests (Section 12.8):

N-back

Tower of London

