Cardiovascular and stress measures (Section 12.9):

Office blood pressure

Pulse wave velocity

Heart rate variability

Blood markers- highly sensitive CRP, interleukin (IL)-6, TNF-alpha and HbA1c

Hair Cortisol

Neurotological tests (Section 12.4):

Vestibular Evoked Myogenic Potentials (VEMP)
Video Hit Impulse Tests (vHIT)
Audiometry
Otoacoustic Emissions (OAE)
Videonystagmography (VNG)
Matted Romberg test
Unterberger test
Vestibular Event Monitoring

Screening, Phenotyping and Explanatory Questionnaires and measures (Appendix B & C):

Insomnia Severity Index (ISI) questionnaire
Weinstein's Noise Sensitivity Scale (WNS) score
Depression Anxiety and Stress Scale (DASS-21)
Kessler 10 (K10)
EYSENCK Personality Questionnaire-Revised
Noise Annoyance Scale
Symptom Visual Analogue Scales
Warwick Edinburgh Mental Well-being Scale
Ethnicity
Medical history
Medication
Sleep Disorders and Patterns
Epworth Sleepiness Scale
Health and Work Performance Questionnaire
Shift work questionnaire
Attitudes on Windfarms
Exit questionnaire

Table 1. Screening and Outcomes Measurements

[figure not shown]
Item	Staff	Screening	Baseline	3month	6month
Screening - online					
Weinstein's Noise Sensitivity Scale (WNS)		X			
Cardiovascular, sleep, or neurological chronic illness			X		
Clinically significant sleep disorders		X			
Major psychiatric disorder		X			
Hypnotic or anti-psychotic medication		X			
Shiftwork Questionnaire		X			
Breastfeeding, Pregnant or planning pregnancy		X			
Child under the age of 5 years		X			
Insomnia Severity Index		X	X	X	X
Epworth Sleepiness Scale			X	X	X
DASS-21			X	X	X
Kessler-10			X	X	X
Attitudes on Wind farms			X		
Exit Questionnaire					X
Screening – home					
Actigraphy and Consensus sleep diary (7 nights)		X			
Audiometry		X			
Clinical Assessments - home					
Sleep and Wake Measurements					
Home 4 EEG channel polysomnography (1 night)			X	X	X
Neurobehavioural and neurocognitive performance			X	X	X
Actigraphy (7 nights prior to PSG)			X	X	X
Sleep Disorders and Patterns Questionnaire			X	X	X
Cardiovascular and Stress measurements					
Height, Weight, Waist circumference			X	X	X
Office Blood Pressure			X	X	X
hsCRP			X	X	X
IL-6			X	X	X
TNF-alpha			X	X	X
Hair cortisol			X	X	X
HbA1c			X	X	X
Pulse wave velocity			X	X	X
Annoyance and Wind Turbine Syndrome measurements					
Visual Analogue Scale questionnaire			X	X	X
Noise Annoyance Scale			X	X	X
Psychological measurements					
EYSENCK Personality Questionnaire-Rev.			X		

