8.1 Enrolment/screening

Screening of suitable participants will be undertaken in two phases. The first phase will be conducted via an online screening questionnaire. The second phase will combine a non-invasive technique (wrist actigraphy and sleep diary) for the at-home measurement of normal sleep/wake cycles and an at home clinical assessment with the study research team.

Phase 1: Online Screening

Online screening procedure is described in 12.3

All participants who attempt stage 1 of screening (i.e. receive a unique login, see 13.2.2) will be assigned with a sequential screening number (i.e. S1, S2 etc)

Phase 2: Home Screening

The home screening procedure is described in 12.3.1

If a potential participant is deemed suitable by the online screening procedure they will be contacted by the study coordinator and a face-to-face screening appointment at their home will be arranged. For 7 days preceding this appointment they will wear an Actiwatch 2 and asked to fill out a sleep diary. Participants will be sent instructions with the device and diary via courier. Actigraphy will be visually checked to ascertain whether the participant has a normal 24 sleep/wake cycle and biologically sufficient sleep (at least an average of 5.5 hours per 24 hours). Sleep diaries will also be kept to correlate with actigraphy data.

At the face-to-face screening at home, participants will have audiometry and those with impaired hearing will be excluded.

If a participant is willing and eligible they will then have the study fully explained to them and will be given the opportunity to ask questions before they give written informed consent to enrol in the study at this visit. They may also make that decision later and return informed consent documents via email, post or in person

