8.3 Infrasonic or Sham speaker installation and monitoring

The acoustic engineer will schedule a visit to the home soon after baseline testing has been completed. At this visit, either infrasonic or sham speakers will be installed into the bedroom of the participant. In addition to the 4 x 600mm cube speakers we will place a monitoring box and 2 microphones in the bedroom.

The acoustic engineer is unblinded and will advise participants that if they have any concerns about the speakers that they should contact him directly and not discuss this with other members of the team who do not know what type of speaker is installed in the bedroom. Additionally, the participants will be informed that their electricity bill may increase and that they will be reimbursed for this expense. Again, this is to be discussed with the unblinded acoustic engineer who installed the speakers and not any other member of the team.

The acoustic engineer will arrange regular visits to the home of participants to check that they speakers are performing as designed and that the monitoring equipment is collecting infrasonic or sham sound exposure information. These visits will be weekly in the first month, then monthly for the next five months or as required. He will download data and bring this back to Woolcock Institute for secure storage.

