12.3.1 Home screening

If shown eligible on the online screening, participants will be contacted by a member of the research team to organise a face to face appointment at home. Prior to the home visit participants will be sent an Actiwatch 2, a painless watch-like device worn around the wrist to monitor sleep and wake cycles and activity patterns (body movement and ambient light). Accompanying the Actiwatch 2, participants will be sent and asked to fill out a sleep diary self-assessing their sleep whilst at home. Participants will be asked to wear the Actiwatch 2 and complete the sleep diary for at least 7 days before coming in to their face-face appointment.

At the face to face home screening the participant will have their hearing tested. Participants will go through various hearing tests (Section 12.4.3)

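### Exclusions 5 and 6 are household states that can change, but Table 1 checks them only at online screening, with no limit on the time to speaker installation

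*Protocol*

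**What the plan says.** Section 5.2, item 5, excludes homes with "Breastfeeding, pregnant or attempting to become pregnant women in the household". Item 6 excludes homes where a child under five lives. Both describe the household, not only the participant.

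Table 1 carries the two criteria as the rows "Breastfeeding, Pregnant or planning pregnancy" and "Child under the age of 5 years". They sit in the online screening block, each with a single mark in the Screening column and none at Baseline, 3 months or 6 months.

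The later steps are:

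- **Home screening (Sections 8.1 and 12.3.1).** "For 7 days preceding this appointment they will wear an Actiwatch 2". At the visit, "At the face to face home screening the participant will have their hearing tested". Section 12.6 adds body measurements and blood pressure.
- **Consent (Section 8.1).** It may be given at that visit, but "They may also make that decision later and return informed consent documents via email, post or in person". No deadline is set.
- **Baseline and installation (Sections 8.2 and 8.3).** "The acoustic engineer will schedule a visit to the home soon after baseline testing has been completed". The equipment then runs continuously for six months (Section 6).

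Section 6.1 lets the investigator withdraw a participant "If any of the study exclusion criteria are diagnosed".

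**The concern.** An entry criterion that can lapse should be confirmed close to the point where it matters, which here is the day the speakers go in. The protocol confirms items 5 and 6 at the earliest point in the sequence, and several steps of open-ended length follow. A pregnancy that was unplanned or unrecognised at screening, a change of plans, or a new resident could make a home ineligible in the meantime, and no scheduled question would show it.

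The protocol gives no reason for items 5 and 6. It does say, in Section 15.1, that infrasound of this kind has not been used experimentally for more than two hours, and for that reason it convenes a safety board. Given that, the protocol's own household exclusions should still hold when a six-month continuous exposure starts. What is at stake is participant and household safety and correct application of eligibility. The efficacy analysis is not in question.

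**Working it through.** The protocol states no figure to reproduce. The check sets the exclusion list against the schedule and each later contact.

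**1. Scheduled checks.** Table 1 has four time points: Screening, Baseline, 3 months and 6 months. The two rows are marked at 1 of 4, and at 0 of the 3 after screening. Other rows are repeated: the Insomnia Severity Index is marked at all four, and DASS-21 and Kessler-10 at the three visits after screening.

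**2. Age of the answer at installation.** The order is online screening, actigraphy, home screening, consent, baseline, installation. Actigraphy takes at least 7 days, so the answer is at least 7 days old. If the 7-night baseline actigraphy in Table 1 is a separate recording, the minimum is 7 + 7 = 14 days. The protocol sets no maximum, and consent returned later by post or email can lengthen the interval.

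**3. Other contacts that might serve as a check.**

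| Contact | Stated content | Asks about items 5 or 6? |
|---|---|---|
| Home screening (8.1, 12.3.1, 12.6) | Actigraphy, diary, hearing, body measurements | Not listed |
| Neurotological history (12.4.1) | Participant's history relevant to that examination | Not listed |
| Engineer visits (8.3) | Equipment and exposure data | Not listed |
| Adverse events (16) | Collected throughout | No household question named |
| Questionnaires shown in Appendices B and C | Noise sensitivity, sleep, mood, symptoms, medical history, medication | None on pregnancy, breastfeeding or young children at home |

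Section 8.1 speaks of a willing and eligible participant at the home visit. That implies a judgement of eligibility, but it names no repeat of these two items.

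**4. The withdrawal rule.** Section 6.1 expects that an exclusion may come to light after enrolment. For items 5 and 6 that depends on someone volunteering the fact or on staff noticing it. By contrast, Appendix C provides for medications to be asked about at the baseline home visit. Other members of the household have no study visit of their own.

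**5. Before and during exposure.** Before installation, none of the contacts in step 3 is a confirmation. During exposure the same contacts offer some chance of detection. The gap is therefore clearest before installation and weaker afterwards.

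**The case against.** The strongest reply is that nothing here is misstated. Section 5.2 and Table 1 agree, entry criteria are checked at entry, and a repeat question is visit-checklist detail. The consent pages are not in the document reviewed and may oblige participants to report a pregnancy or a new child in the home. Section 5.1 shows that this trial does use consent for household undertakings, since it bars anyone under 18 from sleeping in the speaker bedroom. Staff and the engineer enter the home often, adverse events are collected throughout, and Section 6.1 allows withdrawal at any time. Women attempting to conceive are already excluded. Other exclusions, such as shift work and planned absence, are not re-asked either.

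Much of this stands. It shrinks the gap during exposure and keeps the severity low. It does not supply a confirmation before the speakers go in. A reporting duty relies on people volunteering information, and the bedroom rule does not address pregnancy or a young child living elsewhere in the home. Eligibility checks and the visit schedule are protocol matters, and Table 1 fixes these two at one early point.

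A reader might infer more, and the document does not support it:

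- **That households go unwatched for six months.** The contacts above count against this.
- **That no reporting duty exists.** The consent pages cannot be read, so this is unknown.
- **That the pregnancy row asks only about the participant because it omits the household.** It is a short label, and the wording of the screening question is not shown.

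**Conclusion.** The point holds as a low-severity gap in the schedule. Items 5 and 6 are checked once, at least 7 days before installation and with no upper limit, so a home that has ceased to meet Section 5.2 could still receive speakers. During exposure the gap is partly covered.

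The number of homes affected cannot be estimated: the document gives no rate of pregnancy or household change and no typical time from screening to installation. Any figure for the total unchecked period beyond the stated minimum would rest on an assumed gap, so none is offered. For item 6, what remains after baseline is small: mainly a child moving in, or a birth from a pregnancy missed at screening. It would be going too far to read this as a threat to the trial's result, because nothing in the protocol links these two criteria to power, type I error or WASO.

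**What to change.** In Table 1, add a mark at Baseline for both rows, worded for the household as in Section 5.2. The answer is needed before installation, and preferably before randomisation so that a positive answer does not become a post-randomisation exclusion. State that a household with a positive answer is not randomised or, if already randomised, does not receive speakers.

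At 3 months, add one question, identical in both arms, on pregnancy or breastfeeding in the household and on any child under five who has moved in. Refer positive answers to the investigator for a decision under Section 6.1. If only one change is made, it should be the baseline one.

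The cost is a few minutes at two visits that already include questionnaires, a short edit to Table 1 and Section 6.1, and an occasional exclusion or withdrawal, which Section 6.1 already allows.
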